6.3 Adverse Event Reporting

Any adverse events occurring throughout the duration of this study will be promptly addressed and brought to the attention of the University of Alberta HREB as well as Health Canada if the situation dictates.

If any unseen safety concerns were to arise the protocol would be stopped and reviewed to determine the source of safety concerns. As this study is only observing one step in the treatment of the patient, their hospital care will be continued as required in all cases.

6.4 Adverse Event Follow-up

The direct care team will report any adverse events to the research team. The research team will follow-up with the patients in person or via telephone for the duration of treatment or until the adverse event has resolved. This study will not interfere with the normal care and treatment of these patients either before or after participation in the study.

7 Statistical Plan

7.1 Statistical Methods

As this study is comparing a single experimental group to a control group we will use a standard statistical analysis to compare both the primary outcome of hemostasis and the secondary outcome results of the pain and comfort questionnaire. This is a non-inferiority study and has been powered as such. We will use a chi-square test to determine significance of any difference between the treatment and control group.

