Management of Persistent Epistaxis Using Floseal Hemostatic Matrix

PROTOCOL IDENTIFYING NUMBER 001

PROTOCOL VERSION DATE June 8, 2015

GENERAL INFORMATION

Name and title of the investigators and sub-investigators responsible for the trial with address and phone numbers

[name] [name]

[name] [contact]

[name]

[name] [contact]

[name] BSc.

[name] [contact] [contact]

| Title | Management of Persistent Epistaxis using Floseal Hemostatic Matrix |
|--|---|
| Short Title | Floseal Epistaxis Study |
| Protocol Number | 001 |
| Phase | Phase 4 Clinical Trial |
| Methodology | Randomized open-label Trial |
| Study Duration | 1 Year |
| Study Center(s) | Single-Center, University of Alberta |
| Objectives | We wish to observe the effectiveness of Floseal Hemostatic Matrix in aborting persistent epistaxis with the end of bleeding being our primary outcome. We also wish to include measures of patient comfort and cost analysis of epistaxis treatment. |
| Number of Subjects | 60 |
| Diagnosis and Main Inclusion Criteria | Adult patients presenting for Otolaryngology Head and Neck Surgery consult in the Emergency Department with persistent epistaxis. |
| Study Product, Dose, | Floseal Hemostatic Matrix, 5mL |
| Duration of administration | 30 Minutes |
| Reference therapy | Standard nasal packing using gauze by a trained Otolaryngology resident |
| Statistical Methodology | This study is powered based on a non-inferiority analysis to compare the efficacy of Floseal at achieving hemostasis. We will perform standard chi-square statistical analysis to determine the significance of these outcomes. |

Study Summary

Table of Contents

| 1 | | BACKGROUND | .1 |
|----|-----|---|---------------------|
| | 1.1 | INVESTIGATIONAL AGENT | .1 |
| | 1.2 | PRECLINICAL DATA | .1 |
| | 1.3 | Risk/Benefits | .1 |
| | 1.4 | DOSE RATIONALE | .1 |
| | 1.5 | TRIAL CONDUCT | .1 |
| | 1.0 | POPULATION. | .2 |
| | 1./ | LII EKA I UKE | .2 |
| 2 | | TRIAL OBJECTIVES | .2 |
| 3 | | TRIAL DESIGN | .2 |
| | 3.1 | PRIMARY STUDY ENDPOINTS/SECONDARY ENDPOINTS | .2 |
| | 3.2 | Study Design/Type | .2 |
| | 3.3 | RANDOMIZATION | .3 |
| | 3.4 | TRIAL TREATMENT | .3 |
| | 3.5 | DURATION | .3 |
| | 3.6 | DISCONTINUATION | .4 |
| | 3.7 | DATA IDENTIFICATION | .4 |

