3.1 Primary Study Endpoints/Secondary Endpoints

The primary endpoint of this study will be when hemostasis is achieved and there is no longer any active bleeding from the nasal cavity. Our secondary endpoint will be two days following the intervention when we obtain the telephone questionnaire results from the patients about pain level and comfort of the treatment.

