7.5 Deviation Reporting

In the case that any changes to the statistical analysis of this trial may arise they will be fully disclosed. Any deviation from the original statistical plan will be amended and justified in the protocol and in the final report.

8 Direct Access to Source Data/Documentation

Throughout the study if direct access data is required for audit or other trial-related monitoring, it can be obtained by written request to [name]. This includes access by any regulatory agency such as the University of Alberta HREB.

9 Quality Control and Quality Assurance

Data from the direct care team will be obtained in paper form and be scanned or otherwise transferred to electronic data kept on the research computer. Interim analysis will be done by the research team to ensure that data collection is continuing as per the protocol. The study coordinator ([name]) will review that data obtained following each patient enrolled in the study and ensure that it is being recorded in compliance with this protocol and good clinical practice requirements.

10 Ethical Considerations

This study will be conducted according to Canadian and international standards of Good Clinical Practice for all studies. Applicable government regulations and University of Alberta research policies and procedures will also be followed.

This protocol and any amendments will be submitted to the University of Alberta HREB for formal approval to conduct the study. The decision of the HREB concerning the conduct of the study will be made in writing to the investigator.

All subjects for this study will be provided a consent form describing this study and providing sufficient information for subjects to make an informed decision about their participation in this study. This consent form will be submitted with the protocol for review and approval by the HREB. The formal consent of a subject, using the HREB-approved consent form, will be obtained before that subject is submitted to any study procedure. This consent form must be signed by the subject or legally acceptable surrogate, and the investigator-designated research professional obtaining the consent.

11 Data Handling and Record Keeping

For confidentiality purposes all data for this study will be coded and de-identified and kept on an encrypted secured database in the personal office of [name].

12 Supplements

Comfort Questionnaire

Patient Name: _____ Researcher Filling out this form: _____

In Person

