Statistical Analysis Plan

Title of Study: Management of Persistent Epistaxis Using Floseal

Hemostatic Matrix

Protocol ID: 6601059

Date of Document: August 22, 2015

Date Modified: October 12, 2018

Sample Size:

An *a priori* sample size was calculated using a non-inferiority limit (d) set at 25%, significance level (α) of 5% and power of 80%. We assumed that success in each group will be approximately 93% based on the literature examining anterior nasal packing in ideal conditions and considering our selection criteria in the Floseal® (Baxter, USA) population. Attrition will be assumed to be 0% due to the short duration of treatment. This should yield 26 participants with 13 patients in each study arm.

Statistical Analysis of Clinical End-points:

This is a non-inferiority trial. A non-inferiority design was chosen due to the anticipated improvement in patient comfort and potential decreased cost thus making the experimental arm a preferred option if non-inferiority can be demonstrated in terms of hemostasis. Further, based on existing literature we do not anticipate a significant difference in terms of efficacy between these two groups. All dichotomous categorical variables will be analyzed by means of the Fisher's exact test. Mean age, CCI and VAS pain scores will be compared using the non- parametric Mann-Whitney U Test.

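### No test is assigned to a graded comfort answer in the SAP, and the protocol's only named test, chi-square, would lose power on such an item by an amount that depends on the number of levels

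*Protocol*

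**What the plan says.** Protocol 3.1 makes the secondary endpoint the 48-hour "telephone questionnaire results from the patients about pain level and comfort of the treatment". Pain and comfort are named as two things.

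Protocol 7.1 places hemostasis and "the secondary outcome results of the pain and comfort questionnaire" under one standard analysis and names one test: "We will use a chi-square test to determine significance of any difference between the treatment and control group". It does not say which chi-square test is meant. The Study Summary has similar wording: "We will perform standard chi-square statistical analysis to determine the significance of these outcomes".

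The SAP, dated after the protocol and modified in 2018, does not mention chi-square. It has two rules: "All dichotomous categorical variables will be analyzed by means of the Fisher's exact test", and "Mean age, CCI and VAS pain scores will be compared using the non- parametric Mann-Whitney U Test". Comfort appears in the SAP only in the justification of the non-inferiority design, where better comfort is the first expected advantage of Floseal. No test is given for a comfort score or for ordered categories in general.

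The "Comfort Questionnaire" in Protocol Section 12 breaks off after its header in the reviewed text. The number and format of its items are therefore unknown here. That is a limit of this review and not a fault of the plan.

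**The concern.** The argument for Floseal leans on comfort. Protocol Section 2 says that with equal effectiveness, much better comfort could make it the favourable treatment. Section 7.2 gives quantifying the secondary benefits as the reason for choosing this trial type. Yet neither SAP rule clearly reaches a separate graded comfort item, and the only test that any document names for the questionnaire as a whole is chi-square.

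A Pearson chi-square on a table of two arms by K levels gives the same result however the levels are ordered. It spreads its power over K − 1 degrees of freedom, whereas a shift towards greater comfort is a one-directional effect that a rank test targets. With few patients the cells are also small. A real comfort benefit could be missed in data where a rank test would find it.

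The silence has a second cost. In an open-label trial, leaving the test unnamed means a graded answer could be cut into two groups and sent to Fisher's test, tested by chi-square, or ranked, with the choice made after the data are seen.

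**Working it through.** **1. The plan's own figure.** The documents give no power or sample size for comfort. The SAP's sample size is for hemostasis: 93% success in both arms, margin 25%, α 5%, power 80%. With one-sided α of 0.05:

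n per arm = (1.645 + 0.842)² × 2 × 0.93 × 0.07 / 0.25² = 6.18 × 0.1302 / 0.0625 = 12.9, so 13 per arm and 26 in total.

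This reproduces the SAP. The protocol plans 30 per arm (Section 7.2). Both sizes are used below.

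**2. Which stated test reaches the comfort answer?**

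| Format of comfort item | Stated test | Loss |
|---|---|---|
| Yes/no | Fisher's exact (SAP) | none |
| Captured by the VAS pain score | Mann-Whitney (SAP) | none |
| Separate graded item | none in the SAP; chi-square in Protocol 7.1 | see steps 3 to 5 |

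**3. Large-sample comparison.** Suppose the ordered test (1 df, two-sided 0.05) has 80% power. Its noncentrality is (1.960 + 0.842)² = 7.85. A chi-square with the same noncentrality on K − 1 df has power 71% (3 levels), 65% (4), 60% (5), 52% (7) and 43% (11).

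**4. Simulation at the planned sizes.** Assumptions, none of them in the documents: control answers spread evenly over K levels, so P(level ≤ k) = k/K; in the other arm the odds of every cumulative split are multiplied by the odds ratio (OR). For K = 5 and OR 5 the control cumulative probabilities 0.2, 0.4, 0.6 and 0.8 become 0.556, 0.769, 0.882 and 0.952. Each simulated trial was tested by Pearson chi-square and by tie-corrected Mann-Whitney, two-sided 0.05, with 3,000 trials per setting. Relative loss is 1 − (chi-square power / rank power); for example 1 − 0.318/0.577 = 45%.

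| Levels | 13 per arm, OR 5: chi-square / rank | Relative loss | 30 per arm, OR 3: chi-square / rank | Relative loss |
|---|---|---|---|---|
| 3 | 0.426 / 0.532 | 20% | 0.491 / 0.603 | 19% |
| 4 | 0.381 / 0.561 | 32% | 0.454 / 0.637 | 29% |
| 5 | 0.318 / 0.577 | 45% | 0.422 / 0.661 | 36% |
| 7 | 0.240 / 0.583 | 59% | 0.367 / 0.661 | 44% |
| 11 | 0.133 / 0.604 | 78% | 0.246 / 0.663 | 63% |

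The simulation error of each power is at most √(0.5 × 0.5 / 3000) = 0.9 percentage points (one standard error). A repeat with 40,000 trials per setting agreed within 3 points throughout. Another run of the same settings at 30 per arm gave 41% against 62% (5 levels) and 26% against 69% (11 levels), within 4 points of the table. With two levels there is no loss.

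**5. Sensitivity to the effect.** Larger effects narrow the gap. At five levels, 13 per arm and OR 8, power is 0.505 against 0.778 (loss 35%); at 30 per arm and OR 4 it is 0.627 against 0.838 (loss 25%). A smaller effect widens it: at five levels, 13 per arm and OR 3, it is 0.171 against 0.325 (loss 47%).

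**6. Small cells.** With five evenly used levels, the expected count per cell is 13/5 = 2.6 or 30/5 = 6. With 11 levels at 13 per arm it is 13/11 = 1.2. There the chi-square rejects in only 1.5% of trials with no effect, against 4.8% for the rank test, so part of the loss in that row comes from sparse data.

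**The case against.** The strongest objection is that the point depends on a questionnaire that cannot be seen. The protocol treats pain and comfort as one questionnaire, no visible protocol section mentions a VAS, and the SAP's VAS pain score may be that questionnaire's graded output. If so, Mann-Whitney already applies. This stands, and it makes the point conditional.

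A reader might infer that chi-square is the settled analysis for comfort. The documents do not show that. The SAP is the later document, never names chi-square, and no text says that protocol tests apply where the SAP is silent. Nor is the SAP limited to yes/no variables and VAS pain: it also assigns Mann-Whitney to age and CCI, so every non-dichotomous variable it lists gets a rank test. That pattern makes a return to chi-square less likely, but it does not assign a test to comfort. The Study Summary sentence is weak support, because it directly follows a sentence about hemostasis and may refer only to that. A chi-square test for trend would use the order, and 7.1 does not exclude one.

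A reader might also take one figure, such as a loss of half the power, as the size of the problem. It is neither a bound nor typical: the loss runs from nil to well over half with the number of levels and the effect.

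Finally, comfort is a secondary endpoint with no stated power, hemostasis is primary, and a bare Mann-Whitney p-value shows the size of a benefit no better than chi-square does. All three are fair; the last is why the fix asks for an estimate.

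**Conclusion.** The point holds conditionally. The SAP assigns no test to a separate graded comfort answer, and the only test named anywhere for the questionnaire as a whole is an unspecified chi-square. If the comfort items are yes/no or are captured by the VAS pain score, there is no loss.

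If they are graded and an unordered chi-square is used, the relative loss of power in the two main settings is about 19 to 20% at three levels, 36 to 45% at five and 63 to 78% at 11. This rests on an assumed proportional-odds benefit, evenly spread control answers, odds ratios of 5 (13 per arm) and 3 (30 per arm), and two-sided 0.05. The documents give none of the level counts, answer distributions or odds ratios. The direction of the result, that an ordered test does better against a shift over three or more levels, held at every odds ratio tried.

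**What to change.** Before the comfort data are compared by arm:

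- **SAP.** Add that any graded comfort response is analysed as ordered data by the Mann-Whitney test (tie-corrected or exact). Report it with an effect estimate and 95% CI: the probability that a Floseal patient has a better score than a packing patient, or a proportional-odds ratio.
- **Protocol 7.1.** Reword so that the chi-square sentence no longer applies to the questionnaire and the section agrees with the SAP. Do not simply delete the sentence: it also carries the test named for hemostasis, which the SAP gives to Fisher's exact test. Make clear in the Study Summary which outcomes its chi-square sentence covers. Section 7.5 already commits to amending and justifying changes to the statistical plan in the protocol.

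The cost is one SAP sentence and a protocol wording edit, with no effect on data collection or patients. If every item turns out to be yes/no, the added sentence simply does not apply. One trade-off is that a rank test is less sensitive than an unordered test to a difference that is not a shift, such as more answers at both extremes. The plan's stated expectation is an improvement in comfort, so a shift is the effect to target.

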7.2 Subject Population(s) for Analysis

We hope to have 60 patients total enrolled in this study (30 Floseal and 30 control). This sample size was chosen to provide the powering listed below. This level of significance is based on a non-inferiority trial. We chose this trial type because we seek to quantify the secondary benefits for this treatment, which is already in use. All randomized subjects will be included in the statistical analysis based on an intention-to-treat protocol.

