4.3 Subject Withdrawal

Patients will be undergoing all aspects of the study under the supervision of a physician or research coordinator and will therefor be encouraged to express any concerns they have so they can be addressed as promptly as possible. We will minimize risk by providing the physicians involved with the most training possible to ensure placement of the treatment is done as easily and accurately as it can be. Patients who wish to withdraw from the study will be able to do so at any time and will be informed of this upon obtaining consent for the study. They will be instructed to speak with any member of the direct care or research team to withdraw him or herself from the study. Patients will not be replaced as this study has a rolling enrollment and we will continue until we acquire the proper number of participants. Data from the withdrawn participants will be discarded, however we will keep the record of the patient themselves and follow-up with them as we would any other patient in the study (if they are willing) to monitor for any adverse events and ensure patient safety.

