5.1 Efficacy Parameters

Efficacy of the Floseal Hemostatic Matrix will be determined by observing whether patients receiving either the Floseal or control treatment require additional measures to abort bleeding. Our primary endpoint is hemostasis, however if hemostasis is not adequately achieved, as determined by the OHNS resident providing direct care, than additional measures will be taken to abort bleeding and this will signify our primary endpoint.

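### The non-inferiority claim rests on an intention-to-treat analysis alone, with no per-protocol set, and the protocol's own withdrawal rule contradicts that analysis set.

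*Protocol*

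**What the plan says.** Both documents describe a non-inferiority trial. Protocol section 7.1 states "This is a non-inferiority study and has been powered as such", and the SAP states "This is a non-inferiority trial".

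On who is analysed, protocol section 7.2 says "All randomized subjects will be included in the statistical analysis based on an intention-to-treat protocol". The SAP names no analysis population. Neither document mentions a per-protocol set, an as-treated set or a sensitivity analysis.

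Protocol section 4.3 points the other way on withdrawals: "Data from the withdrawn participants will be discarded".

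On the outcome, section 5.1 judges efficacy by "observing whether patients receiving either the Floseal or control treatment require additional measures to abort bleeding". If hemostasis is inadequate, "additional measures will be taken to abort bleeding and this will signify our primary endpoint". A patient who is treated and then rescued is therefore a failure in the assigned arm.

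**The concern.** In a superiority trial, intention-to-treat is usually the cautious choice, because departures from assigned treatment pull the arms together and make a difference harder to show. In a non-inferiority trial the same pull makes the claim easier to reach. With only an intention-to-treat result, a reader cannot tell whether similar success rates mean that Floseal works as well as packing, or that some patients did not receive what they were assigned.

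Counting rescue as failure closes one route to this dilution. Two remain:

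- **Non-receipt.** Bleeding stops between randomization and application, and the patient counts as a success for a product that was never used. Eligibility is checked first, then consent is taken by someone outside the care team (section 4.4), then the envelope is opened, and Floseal needs preparation before use (section 3.4).
- **Crossover.** The other arm's treatment is given first. The trial is open-label (section 3.3), and residents of the same service deliver both treatments (section 4.4).

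Neither document says how such patients are to be identified or reported. At 13 per arm, one patient is 1/13 = 7.7% of an arm. The contradiction over withdrawn patients means that the one named population is itself not settled.

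**Working it through.** **1. Reproduce the plan's sample size.** SAP inputs: 93% success in both arms, margin 25 points, α 5%, power 80%, attrition 0%. The SAP does not say whether α is one- or two-sided.

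n per arm = (z₀.₉₅ + z₀.₈₀)² × [0.93 × 0.07 + 0.93 × 0.07] / 0.25² = (1.645 + 0.842)² × 0.1302 / 0.0625 = 12.9, which rounds up to 13 per arm and 26 in total.

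This matches the SAP, so one-sided 5% is used below. One-sided 2.5% would give 17 per arm.

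**2. Set the null case.** True success is 93% on packing and 93 − 25 = 68% on Floseal, so Floseal is inferior by exactly the margin. Any declaration of non-inferiority is then false.

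**3. Choose a test.** The documents name only chi-square and Fisher's exact tests, with no confidence limit set against the margin, so a test has to be assumed. The score test is

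Z = (p̂_T − p̂_C + 0.25) / √{[p̃_T(1 − p̃_T) + p̃_C(1 − p̃_C)] / 13},

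where the p̃ are the maximum-likelihood rates under p̃_T = p̃_C − 0.25. Non-inferiority is declared if Z > 1.645. The rate is the sum of the binomial probabilities of all 14 × 14 outcome pairs that meet this rule.

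**4. Dilute the rates.** Let f be the assumed share of deviating patients.

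- Non-receipt, both arms: p_T = (1 − f)0.68 + f; p_C = (1 − f)0.93 + f.
- One-way crossover (Floseal patients get packing first): p_T = (1 − f)0.68 + 0.93f; p_C = 0.93.
- Two-way crossover: p_T as in one-way; p_C = (1 − f)0.93 + 0.68f.

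Example at f = 0.10. Non-receipt gives 71.2% versus 93.7%, a gap of 22.5 points. One-way crossover gives 70.5% versus 93.0%, also 22.5 points. Two-way crossover gives 70.5% versus 90.5%, a gap of 20.0 points.

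**5. False non-inferiority rate, 13 per arm, 25-point margin.**

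| Assumed f | Non-receipt | One-way crossover | Two-way crossover |
|---|---|---|---|
| 0% | 4.0% | 4.0% | 4.0% |
| 5% | 4.8% | 4.8% | 5.7% |
| 10% | 5.7% | 5.7% | 7.8% |
| 20% | 8.0% | 7.9% | 13.5% |

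**6. Check with other methods.** The unpooled normal approximation starts at 5.0%. At f = 10%/20% it gives 7.1%/9.8% one-way and 9.5%/16.1% two-way. An exact calculation with the Newcombe interval starts at 6.0% and gives 8.2%/11.0% one-way and 11.2%/18.5% two-way. The direction is the same throughout; the level depends on the test.

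**7. Protocol design.** This is 30 per arm with a 5-point margin, borrowing 93% from the SAP because the protocol gives no success rate. The score-test rate is 5.5% at baseline. At f = 10%/20% it is 6.1%/6.7% for non-receipt and 7.1%/9.0% for two-way crossover.

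**8. Sensitivity to one patient.** With the score test at 13 per arm, 12/13 on Floseal versus 12/13 on packing declares non-inferiority, and 11/13 versus 12/13 does not.

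**9. The discard rule.** Take 11/13 on Floseal and 13/13 on packing. The deficit is 100 − 84.6 = 15.4 points. If one of the two Floseal failures withdraws and that patient's data are discarded, the result is 11/12 and the deficit is 100 − 91.7 = 8.3 points.

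**The case against.** The best defence is that this trial gives little room for deviation. Treatment is one application by a trained resident, with the envelope already in the treatment room (section 3.3). Patients must have ongoing bleeding to be eligible (section 4.1), and a resident checks the criteria before consent and randomization (section 3.2). The SAP assumes 0% attrition. One deviating patient does little on average: at f = 1/13, one-way crossover gives 5.3% and two-way gives 6.8%. This largely stands. It limits the size of the problem but does not show that deviations will be absent, and the attrition figure concerns dropout, not adherence.

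A second defence is that a per-protocol analysis is not automatically conservative, since it excludes patients after randomization. This also stands. It is a reason to report both sets, not to replace intention-to-treat.

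Four stronger readings are tempting, and the documents do not support them:

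- **Rescued patients dilute the comparison.** They do not: under section 5.1, needing additional measures is the failure outcome.
- **Ineligible patients, such as those on a blood thinner (section 4.2), necessarily dilute it.** Such a patient still receives the assigned product. If the 25-point gap holds in these patients, the rate at 13 per arm stays at 4.1% to 4.3%. With a wider gap (30% versus 70%, for illustration) it falls to 3.4% or 2.9%.
- **Inflation is larger with the protocol's 30 per arm.** That is so only if the protocol's sample size is joined to the SAP's 25-point margin, a combination that neither document plans.
- **The plan is purely intention-to-treat.** Section 4.3 prevents that reading as well.

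**Conclusion.** The point holds, at modest size. A non-inferiority claim is planned on one analysis population, with nothing to show whether departures from assigned treatment produced it, and sections 4.3 and 7.2 disagree about who is in that population. On the SAP design the false non-inferiority rate rises from 4.0% to between 4.8% and 5.7% at 5% deviation, 5.7% and 7.8% at 10%, and 7.9% and 13.5% at 20%, depending on the type of deviation.

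These figures assume a true deficit equal to the margin, a score test at one-sided 5%, and deviation rates that are hypothetical. The documents give no rate, and with full adherence there is no inflation. A reader might infer that the planned analysis is likely to yield a false claim; that does not follow. The case for change is that the safeguard is standard and cheap, and that a single patient can decide the result at this sample size.

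**What to change.** In section 7.2 and in the SAP:

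1. Keep intention-to-treat, defined as all randomized patients in their assigned arm. Reconcile section 4.3 with it, so that data collected before withdrawal are kept and analysed.
2. Add a per-protocol set, defined before data lock: eligible patients whose first treatment was the assigned one, with rescue still counted as failure.
3. Report the confidence interval for the difference in success in both sets, against one margin. The 5% and 25% limits must first be reconciled, and the interval itself added, because the plan has none.
4. Treat non-inferiority as supported only if both sets agree; otherwise report the result as inconclusive. State that the per-protocol analysis is not automatically conservative, and list the patients excluded from it, with reasons, by arm.

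The cost is a few sentences and one more run of the same analysis. This step changes no sample size, and with full adherence and no ineligible patients the two sets are identical. The downside is a slightly stricter claim and slightly lower power when deviations occur.
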